Therefore, we embarked on this study to investigate in detail the mechanisms involved in ketogenesis, lipolysis and glucagon changes in patients with type 1 diabetes treated with dapagliflozin or Bydureon (exenatide extended release, a long term acting GLP-1 RA) for 12 weeks and in an acute condition of insulinopenia. This study will be the first randomized placebo controlled prospective study investigating the effect of an SGLT-2 inhibitor and Exenatide extended release on ketogenesis.

**Preliminary data:**

***Effect of liraglutide on glucose, glucagon, Ketogenesis and FFA I type 1 diabetes***

[figure not shown]
[figure not shown]
Sixty-three patients with type 1 diabetes were randomized to placebo (17) or liraglutide 0.6 mg (18), liraglutide 1.2 mg (13) and liraglutide 1.8 mg (15) treatment for 12 weeks. There was a statistically significant decrease in average blood glucose concentrations in patients randomized to 1.2 and 1.8 mg groups as compared with placebo. HbA1c fell by 0.78% in 1.2 mg group ( $7.84\pm 0.17\%$  to  $7.06\pm 0.15\%$  ( $p<0.0001$ )) and by 0.42% in 1.8 mg group ( $7.41\pm 0.15$  to  $6.99\pm 0.15$  ( $p=0.001$ )). Basal and bolus insulin doses fell in both 1.2 and 1.8 mg groups. Fasting plasma FFA fell significantly in the 1.8mg group from  $0.55\pm 0.07$  to  $0.45\pm 0.05$  mM, ( $p<0.05$ , Figure 1A). There was no significant change in fasting levels of glucagon following any treatment compared to placebo group while at the end of 12 weeks, the area under curve (AUC) for the HFHC meal induced increase in glucagon was lower by  $47\pm 12\%$  and  $72\pm 12\%$  in the 1.2mg and 1.8mg groups, respectively ( $p<0.05$  for both as compared to 0 week response, Figure 1B). Overall the suppressive effect of liraglutide on postprandial glucagon was dose dependent. There was no significant change in fasting or postprandial concentrations of ketone bodies (acetoacetate acid and  $\beta$ -hydroxybutyrate) following liraglutide treatment.

**Figure 1:** Change in (A) FFA concentrations following meal challenge before and following 12 weeks of liraglutide 1.8mg treatment and (B) change in AUC of glucagon change following meal challenge before and following 12 weeks of different doses of liraglutide in patients with type 1 diabetes. \*= $P < 0.05$  between groups as indicated.

## 4.0 Study Design

### 4.1 Describe and explain the study design (e.g. case-control, cross-sectional, ethnographic, experimental, interventional, longitudinal, observational).

*Response:* The first 60 patients (cohort 1) will be involved in a single center, prospective, double blind, randomized, placebo –controlled in a parallel design study. The last 20 patients (cohort 2) will be enrolled into a single centered, prospective, randomized, open labeled study. The study will be conducted at the Diabetes – Endocrinology Center of Western New York under the direction of [name], M.D, [name], MD, [name] and [name], PhD.

In the first cohort, sixty (60) patients with T1D will be enrolled and randomized into 4 groups (15 each) to receive placebo, or dapagliflozin, or exenatide (5µg acutely)/Exenatide extended release (2mg weekly subcutaneous injection, long term), or exenatide (5µg acutely)/Exenatide extended release (2mg weekly subcutaneous injection, long term) and dapagliflozin treatments acutely and for 12 weeks.

The treatment arms of this study are:

1. Placebo Arm: dapagliflozin placebo (oral tablet) and exenatide (5µg acutely)/Exenatide extended release (long term) placebo (subcutaneous injection)
2. Dapagliflozin Arm: dapagliflozin 10mg (oral tablet) and exenatide (5µg acutely)/Exenatide extended release (long term) placebo (subcutaneous injection)
3. Exenatide/Exenatide extended release Arm: subcutaneous injection of Exenatide (5µg acutely)/Exenatide extended release 2 mg weekly injection (long term) and dapagliflozin placebo
4. Exenatide/Exenatide extended release & dapagliflozin Arm: Exenatide (5µg acutely)/Exenatide extended release 2 mg weekly injection (long term) and dapagliflozin 10mg

In the second cohort, twenty (20) patients will be randomized into three groups.

1. Open-label Dapagliflozin
2. Open-label Bydureon/Byetta
3. Open label Bydureon/Byetta and open label Dapagliflozin

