## 10.0 Procedures Involved

10.1 Provide a description of **all research procedures or activities** being performed and when they are performed once a subject is screened and determined to be eligible. Provide as much detail as possible.

*NOTE: This should serve as a blueprint for your study and include enough detail so that another investigator could pick up your protocol and replicate the research. For studies that have multiple or complex visits or procedures, consider the addition of a schedule of events table in in your response.*

*Response:*

The study investigations include evaluation of the acute effects of a single dose of dapagliflozin (10mg), exenatide (5µg), a combination of exenatide and dapagliflozin or placebo under insulinopenic condition and the long term effect under basal conditions before and after 12 weeks treatment with dapagliflozin, Exenatide extended release, a combination of Exenatide extended release and dapagliflozin or placebo on ketogenesis, glucagon and lipolysis. This applies to the first 60 patients in cohort 1. For cohort 2, we will evaluate the acute effects of a single dose of dapagliflozin (10mg), exenatide (5µg), or a combination of exenatide and dapagliflozin under insulinopenic condition and the long term effect under basal conditions before and after 12 weeks treatment with dapagliflozin, Exenatide extended release, or a combination of Exenatide extended release and dapagliflozin on Ketogenesis.

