This will now mark the end of the acute testing phase and the beginning of the 12 weeks treatment phase. If the HbA1c is  $\geq 7.5\%$ ; then no reduction will be made in dose of insulin while if the HbA1c ranges from 7-7.5% then the basal and pre-prandial insulin doses will be reduced by 5%. All patients will be instructed on how to give the single subcutaneous injection of Exenatide extended release (2mg weekly) or Exenatide extended release placebo (for those in cohort 1), or open label drugs (for those in cohort 2), which will be administered at home the next day. Patients will also be provided with 12 oral tablets of either 5mg placebo or 5mg dapagliflozin (depending on their group assignment and cohort) and instructed to consume 1 tablet in the morning on each of the first 4 days and 2 tablets (10 mg) on days 5, 6 and 7 (and for the rest of the 12 weeks thereafter) and to return to the center on day 7. Urine collection container will be provided and patients instructed to collect 24hr urine before their next visit. The patients will be trained to recognize the symptoms of DKA and to self-test ketones daily and if they develop any symptoms consistent with DKA, including nausea, vomiting, fatigue, confusion, or shortness of breath. Information sheet about above information will be provided to participants. Patients will be instructed to measure ketone bodies in urine samples daily with Ketostix (Bayer) and record it in diary provided. If ketone bodies in urine measure +2 or greater ( $>4\text{mM}$  in urine), patients are required to notify the research center. The investigators will collect all necessary information and advise the patient of any steps to mitigate the risk of DKA or to visit the closest emergency department and to inform emergency staff of their participation in a research study.

;

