**Visit 3 (Week 1):** Vitals will be measured and fasting blood and 24hr urine samples will be collected. Carbohydrate intake/insulin injection logs, food diaries, or CGM/pump data will be reviewed and documented. Patients will be provided with 3 weeks supply of Exenatide extended release or Exenatide extended release placebo and 10mg dapagliflozin or placebo tablets depending on their cohort. Urine collection container will be provided and patients instructed to collect 24hr urine before their next visit. Insulin doses will be titrated to target blood glucose between 70-180 mg/dl if possible at all times without having additional hypoglycemia (less than 70 mg/dl). Ketostix will be dispensed and patients will be instructed to measure ketone bodies in a spot urine sample daily and reported as described in visit 2.

**Visit 4 (Week 4):** Patient physical and vitals will be measured, fasting blood and 24hr urine samples will be collected. Carbohydrate intake/insulin injection logs, food diaries, or CGM/pump data will be reviewed and documented. Patients will be provided with 4 weeks supply of Exenatide extended release or Exenatide extended release placebo and 10mg dapagliflozin or placebo tablets depending on their cohort. Urine collection container will be provided and patients instructed to collect 24hr urine before their next visit. Insulin doses will be titrated to target blood glucose between 70-180 mg/dl if possible at all times without having additional hypoglycemia (less than 70 mg/dl). Ketostix will be dispensed and patients instructed to measure ketone bodies in a spot urine sample daily and reported as described in visit 3.

**Visit 5 (Week 8):** Vitals will be measured and fasting blood and 24hr urine samples will be collected. Carbohydrate intake/insulin injection logs, food diaries, or CGM/pump data will be reviewed and documented. Patients will be provided with 4 weeks supply of Exenatide extended release or Exenatide extended release placebo and 10mg dapagliflozin or placebo tablets depending on their cohort. Urine collection container will be provided and patients instructed to collect 24hr urine before their next visit. Insulin doses will be titrated to target blood glucose between 70-180 mg/dl if possible at all times without having additional hypoglycemia (less than 70 mg/dl). Ketostix will be dispensed and patients instructed to measure ketone bodies in a spot urine sample daily and reported as described in visit 3.

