## 11.0 Study Timelines

11.1 Describe the anticipated duration needed to enroll all study subjects.

Response: Accrual is expected to be at the rate of 1 subject weekly, thus we should complete enrollment in approximately 18-20 months. We expect to complete all study activities in 30 months.

11.2 Describe the duration of an individual subject's participation in the study. Include length of study visits, and overall study follow-up time.

Response: 12 Weeks

11.3 Describe the estimated duration for the investigators to complete this study (i.e. all data is collected and all analyses have been completed).

Response: 30 Months

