## 17.0 Data Management and Analysis

17.1 *Describe the data analysis plan, including any statistical procedures. This section applies to both quantitative and qualitative analysis.*

Response: **DATA ANALYSIS**

This is a prospective study to evaluate ketogenic stress before and after 12 week treatment with dapagliflozin and exenatide/Bydureon. The similarities in baseline values between the study groups will be compared using appropriate parametric tests. Transformations of the data on order to meet statistical assumptions may be considered. All statistical analysis will be carried out using SPSS software (SPSS Inc, Chicago, Illinois) based on intention to treat principle. Data will be presented as mean± standard error. *Data will not be imputed to replace missing data and only observed data will used to run the mixed model for repeated measurement (MMRM) analysis. The primary endpoint of the study is to detect a significant difference in the percent change in beta-hydroxybutyrate and acetoacetic acid (total ketone bodies) in the plasma samples following 12 weeks of dapagliflozin treatment compared to placebo. *Fasting samples collected at weeks 0, 1, 4, 8 and 12 will be used for this comparison with values at week 0 considered as baseline. The statistical analysis will be done using MMRM with assigned  $\alpha$  value of 0.05. There is no previous data on effects of dapagliflozin alone on ketone bodies generation in T1D but our preliminary data on 12 weeks treatment with**

dapagliflozin in patients with T1D using insulin and liraglutide shows more than a 2 fold increase in total ketone bodies.

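### Section 17 gives no rule for open-label cohort 2, which has no placebo arm, in the placebo comparisons, and its 20 patients per group do not match the 15 placebo patients in section 4.1

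*Combined protocol and SAP*

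**What the plan says.** Section 4.1 describes two cohorts. For the first: "In the first cohort, sixty (60) patients with T1D will be enrolled and randomized into 4 groups (15 each"; these are double blind and include placebo. The second is described thus: "The last 20 patients (cohort 2) will be enrolled into a single centered, prospective, randomized, open labeled study". On its allocation: "In the second cohort, twenty (20) patients will be randomized into three groups". Those groups are dapagliflozin, exenatide and the combination. There is no placebo group, and the split is not given.

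Section 10.1 also treats the cohorts separately ("This applies to the first 60 patients in cohort 1. For cohort 2, we will evaluate the acute effects of a single dose") but does not say how cohort 2 data will be analysed. Section 11.1 gives the pace: "Accrual is expected to be at the rate of 1 subject weekly, thus we should complete enrollment in approximately 18-20 months".

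Section 17.1 makes the primary comparison the percent change in plasma total ketone bodies on dapagliflozin against placebo. It uses a mixed model for repeated measures (MMRM) on fasting samples at weeks 0, 1, 4, 8 and 12. Several secondary endpoints are also compared with placebo, by t-test or repeated-measures ANOVA. The only statement about who is analysed is this: "All statistical analysis will be carried out using SPSS software (SPSS Inc, Chicago, Illinois) based on intention to treat principle". Section 17.2 assumes a difference of 50%, an SD of at most 50%, 20 patients per group with 15% dropout, 80% power and 80 patients in total. Neither 17.1 nor 17.2 mentions cohort, open-label treatment, pooling or a cohort term.

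**The concern.** There are two linked defects.

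- **The sample size does not fit the design.** All placebo patients come from cohort 1, so there are 15, not 20. This holds whatever is done with cohort 2. Twenty may be a four-arm figure (4 x 20 = 80) that takes no account of how cohort 2 is allocated.
- **The primary analysis set is undefined.** One reading compares 15 with 15, blinded and concurrently randomised. The other compares 15 placebo patients with about 22 on dapagliflozin, some enrolled after placebo randomisation had ended and treated open label. Intention to treat does not decide between them. It keeps patients in their assigned arm, but it does not say whether patients who could never have been assigned placebo belong in a placebo contrast.

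The stated power is at stake, and so is prespecification. Cohort 2 results are visible by arm as they accrue. With no rule in section 17, the decision to pool could be taken after they are known.

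**Working it through.** **Inputs.** Difference 50, SD 50, alpha 0.05, power 0.80, dropout 15% (section 17.2); 15 per arm in cohort 1 and 20 patients over three active arms in cohort 2 (section 4.1). Assumed: a two-sided test and an equal cohort 2 split, 20/3 = 6.67 per arm.

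**1. The plan's own figure.** With difference/SD = 1, a two-sided t-test needs 16.7, so 17 per group. 17/0.85 = 20, and 4 x 20 = 80. The stated 20 reproduces.

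**2. Numbers the design supplies.** Placebo: 15, or 15 x 0.85 = 12.75 after dropout. Dapagliflozin: 15 from cohort 1, or 15 + 6.67 = 21.67 pooled (18.42 after dropout). Pooled share from cohort 2: 6.67/21.67 = 0.308.

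**3. Power by t-test.** Noncentrality = (50/50)/sqrt(1/n1 + 1/n2), df = n1 + n2 - 2.

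| Reading | n1 v n2 | Noncentrality | Power |
|---|---|---|---|
| As planned, after dropout | 17 v 17 | 2.915 | 80.7% |
| Cohort 1 only, no dropout | 15 v 15 | 2.739 | 75.3% |
| Cohort 1 only, after dropout | 12.75 v 12.75 | 2.525 | 67.8% |
| Pooled, no dropout | 15 v 21.67 | 2.977 | 82.5% |
| Pooled, after dropout | 12.75 v 18.42 | 2.745 | 75.6% |

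The difference detectable at 80% power with SD 50 is 53.0 points at 15 v 15 and 57.3 at 13 v 13.

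**4. MMRM contrast at week 12.** The documents give no within-patient correlation. I assumed compound symmetry with correlation 0.3, 0.5 or 0.7 over weeks 1, 4, 8 and 12, and 5% dropout after each of weeks 1, 4 and 8. A patient seen at m visits contributes the inverse of the m x m covariance matrix. The week-12 variance comes from inverting the summed information.

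| Correlation | Cohort 1 only (df 50) | Pooled (df 67) | 20 per arm (df 66) |
|---|---|---|---|
| 0.3 | 70.6% | 78.0% | 82.7% |
| 0.5 | 71.9% | 79.2% | 83.8% |
| 0.7 | 73.5% | 80.7% | 85.1% |

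A contrast averaged over the four visits gives 96.7%, 91.6% and 85.6% for cohort 1 only.

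**5. Cohort-adjusted model.** With arm and cohort terms, all 80 patients and 15% dropout (12.75 per arm in cohort 1, 5.67 in cohort 2), the variance of the dapagliflozin v placebo contrast is 0.1408 SD². Power is 74.7% on 68 - 5 = 63 df. On the same all-arm basis, cohort 1 only gives 69.6% and unadjusted pooling 77.1%.

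**6. Bias if pooled without a cohort term.** Bias = 0.308 x cohort shift. The documents give no shift; assumed shifts of 10 and 25 points (0.2 and 0.5 SD) give 0.308 x 10 = 3.1 and 0.308 x 25 = 7.7 points. Simulated t-tests (13 + 6 v 13, 400,000 runs) give type I error of 5.0% with no shift, 5.3% at 0.2 SD and 6.6% at 0.5 SD.

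**7. Timing.** At one patient a week, cohort 1 fills in 60 weeks (13.8 months) and cohort 2 occupies about weeks 61 to 80 (to 18.4 months).

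**The case against.** - **The shortfall depends on the method.** The primary analysis is an MMRM, not a t-test. Under the pooled reading a week-12 MMRM contrast has 78-81% power, so it passes 80% at a correlation of 0.7. This stands as a limit on the power claim. But a t-test is what reproduces the plan's 20 per group, and on the same MMRM basis 20 per arm gives 83-85%, so the loss against the plan remains.
- **The contrast is not fixed.** All post-baseline visits feed the primary comparison, and a visit-averaged contrast has 86-97% power with cohort 1 alone. This is fair, but the endpoint is worded as change after 12 weeks and no averaged contrast is named.
- **The inputs are described as conservative.** Section 17.2 presents the difference as a conservative estimate and the SD as an upper limit. By the plan's wording, the figures above are results at those limits, not central estimates.
- **The arithmetic behind 20 per group is sound.** True. The error is that section 4.1 does not supply those patients.
- **No bias is demonstrated.** The documents neither state pooling nor give a cohort shift. Several features would limit bias: one centre, one eligibility list, a laboratory endpoint, change from own baseline, a starting insulin change set by HbA1c band, an insulin floor (section 21.1), and a shared insulin target ("Insulin doses will be titrated to target blood glucose between 70-180 mg/dl if possible at all times"). A 10-point shift leaves type I error practically nominal. This stands, so the case does not rest on predicted large bias.

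**Conclusion.** The concern holds; the plan is wrong as written on sample size and silent on the primary analysis set. The first defect needs no assumption about pooling: placebo has 15 patients against the 20 on which power is based. By the t-test that reproduces the plan's figure, power after 15% dropout is about 68% for cohort 1 only and 76% pooled, against 81% for the planned 20 v 20. With a week-12 MMRM the corresponding ranges are 71-74%, 78-81% and 83-85%.

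These results assume a two-sided test, difference and SD both 50, an equal cohort 2 split and, for the MMRM, correlations of 0.3 to 0.7 with evenly spread dropout. A visit-averaged contrast would exceed 80%, so low power is not certain under every contrast. The size of any pooling bias is unknown. The point must still be settled because the population for the primary comparison is undefined and its stated size is not delivered.

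**What to change.** In section 17:

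- State that the primary dapagliflozin v placebo comparison and all other placebo contrasts (MMRM, t-test, repeated-measures ANOVA) use the concurrently randomised, blinded cohort 1.
- Use cohort 2 in comparisons among dapagliflozin, exenatide and the combination, with a cohort term, and give its planned split.
- Report a cohort-adjusted analysis of all 80 patients as supportive, naming its assumption of no treatment-by-cohort interaction.
- Restate sample size and power for 15 v 15, and name the MMRM contrast to which the power refers.

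The cost is wording only, with no new patients or procedures. The downside is a stated power below 80% on the plan's t-test basis (75% without dropout, 68% with it), about 8 points less than unadjusted pooling after dropout (75.6 - 67.8 = 7.8). The sponsor could instead make the cohort-adjusted model primary, at about 75% after dropout. That would also close the gap if prespecified, but it still borrows open-label patients.

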## 5.0 Local Number of Subjects

### 5.1 Indicate the total number of subjects that will be enrolled or records that will be reviewed locally.

*Response:* 80

### 5.2 If applicable, indicate how many subjects you expect to screen to reach your target sample (i.e. your screen failure rate).

Response: All screened and qualified patients will be enrolled and randomized

5.3 *Justify the feasibility of recruiting the proposed number of eligible subjects within the anticipated recruitment period. For example, how many potential subjects do you have access to? What percentage of those potential subjects do you need to recruit?*

Response: The Diabetes and Endocrinology Center of WNY is the largest Diabetes center in the WNY area, seeing between 60 to 100 type 1 diabetic patient every month. Therefore, majority of recruited patients are our clinic patients. We do recruit a few patients through advertisement and researchmatch.org. These sources will suffice to recruit the needed number to subjects.

## 6.0 Inclusion and Exclusion Criteria

6.1 *Describe the criteria that define who will be **included** in your final study sample.*

*NOTE: This may be done in bullet point fashion.*

*Response: **Inclusion Criteria***

- Type 1 Diabetes for at least 1 year on stable use of continuous subcutaneous insulin infusion (CSII) or multiple (four or more) injections of insulin per day for last 3 months.
- HbA1c of 7-10% (inclusive)
- Ages 18-65 years (inclusive of ages 18 and 65)
- BMI  $\geq$  22 kg/m^2.
- Well versed in CHO counting.

6.2 *Describe the criteria that define who will be **excluded** from your final study sample.*

*NOTE: This may be done in bullet point fashion.*

*Response: **Exclusion Criteria***

- Inability to give informed consent
- Inability or refusal to comply with protocol
- Use of GLP-1 Receptor Agonists in the last 3 months or DPP-IV and SGLT-2 inhibitors therapy in the last 1 month.
- Risk for pancreatitis (e.g., history of gallstones, alcohol abuse, and hypertriglyceridemia)
- History of pancreatitis and or chronic pancreatitis
- Coronary event or procedure (myocardial infarction, unstable angina, coronary artery bypass, surgery or coronary angioplasty) or stroke in the previous 3 months.
- Congestive Heart Failure class III or IV or tachyarrhythmia.

- Hepatic disease: Severe hepatic insufficiency and/or significant abnormal liver function defined as:
  1. Aspartate aminotransferase (AST) >3x upper limit of normal (ULN) and/or alanine aminotransferase (ALT) >3x ULN
  2. Total bilirubin >2.0 mg/dL (34.2 µmol/L)
  3. Positive serologic evidence of current infectious liver disease including Hepatitis B viral antibody IGM, Hepatitis B surface antigen and Hepatitis C virus antibody
  4. Liver function tests more than 3 times the upper limit of normal
- Renal impairment (e.g., serum creatinine levels  $\geq$ 1.4 mg/dL for women, or eGFR <60 mL/min/1.73 m^2) or history of unstable or rapidly progressing renal disease or end stage renal disease.
- History of unexplained microscopic or gross hematuria, or microscopic hematuria at visit 1, confirmed by a follow-up sample at next scheduled visit.
- HIV positive
- History of gastroparesis
- History of medullary thyroid carcinoma or MEN 2 syndrome
- History of recurring UTI
- Uncontrolled thyroid disease (documented normal TSH), Cushing's syndrome, congenital adrenal hyperplasia or hyperprolactinemia.
- Prior history of a malignant disease requiring chemotherapy or patients with a prior history of bladder cancer regardless of treatment
- Alcoholism or drug addiction.
- Hypertriglyceridemia (>400 mg/dl).
- Any other life-threatening, non-cardiac disease
- Uncontrolled hypertension (BP > 160/95 mm of Hg)
- Patients with hypotension or at risk for volume depletion due to co-existing conditions or concomitant medications, such as loop diuretics or recently donated >500ml of blood should have careful monitoring of their volume status
- Pregnant or breastfeeding patients or patient not willing to use two barrier method contraception during study period (unless sterilized or have an IUD)
- Use of hormonal medications, anti-obesity drugs or weight loss medications (prescription or OTC) and medications known to exacerbate glucose tolerance (such as isotretinoin, GnRH agonists, glucocorticoids, anabolic steroids, C-19 progestins) stopped for at least 8 weeks. Use of anti-androgens that act peripherally to reduce hirsutism such as 5-alpha reductase inhibitors (finasteride, spironolactone, flutamide) stopped for at least 4 weeks
- Presence of hypersensitivity to dapagliflozin or other SGLT2 inhibitors (e.g. anaphylaxis, angioedema, exfoliative skin conditions)
- Known hypersensitivity or contraindications to use GLP1 receptor agonists (exenatide, liraglutide)
- Known hypersensitivity to heparin/ IV catheter equipment.
- Eating disorders (anorexia, bulimia) or gastrointestinal disorders
- Having a history of bariatric surgery

- Debilitating psychiatric disorder such as psychosis or neurological condition that might confound outcome variables
- Use of an investigational agent or therapeutic regimen within 30 days of study
- Participation in any other concurrent clinical trial

6.3 Indicate specifically whether you will include any of the following special populations in your study using the checkboxes below.

**NOTE: Members of special populations may not be targeted for enrollment in your study unless you indicate this in your inclusion criteria.**

Response: NA

- Adults unable to consent
- Individuals who are not yet adults (infants, children, teenagers)
- Pregnant women
- Prisoners

6.4 Indicate whether you will include non-English speaking individuals in your study. **Provide justification if you will exclude non-English speaking individuals.**

*In order to meet one of the primary ethical principles of equitable selection of subjects, non-English speaking individuals may **not** be routinely excluded from research as a matter of convenience.*

*In cases where the research is of therapeutic intent or is designed to investigate areas that would necessarily require certain populations who may not speak English, the researcher is required to make efforts to recruit and include non-English speaking individuals. However, there are studies in which it would be reasonable to limit subjects to those who speak English. Some examples include pilot studies, small unfunded studies with validated instruments not available in other languages, studies with numerous questionnaires, and some non-therapeutic studies which offer no direct benefit.*

Response: We have no non-English speaking patients in this population. We have patients that English is a second language, but they are able to read, write and understand it. This population is less than 10% of the total population.

